The effectiveness of repetitive transcranial magnetic stimulation (rTMS) on improving sleep quality in adults without serious mental illness

Repetitive Transcranial Magnetic Stimulation (rTMS) is a non-invasive brain stimulation technique that uses magnetic fields to modulate neural activity in targeted brain regions. Over the years, rTMS has shown promise in treating various mental health conditions, including depression^{1,2}, obsessive-compulsive disorder (OCD)^{3,4} and clinical insomnia^{5,6,7}.

Sleep is a fundamental component of overall health and well-being, playing a crucial role in cognitive function, emotional regulation, and physical health. However, sleep complaints are common, even among otherwise healthy adults, often leading to reduced quality of life and increased health risks. The prevalence of poor sleep quality can be attributed to a variety of factors, including stress, lifestyle habits, and environmental disturbances.

Prior research on rTMS and sleep has primarily focused on clinical populations, particularly individuals with insomnia or sleep disorders comorbid with other health conditions. While these studies have provided valuable insights, there is a burgeoning interest in exploring the effects of rTMS on sleep quality in the general population, specifically targeting those who report sleep complaints but do not meet the criteria for clinical insomnia.

This research proposal aims to investigate the effects of rTMS on sleep quality among healthy adults experiencing subclinical sleep issues. By focusing on this population, we hope to uncover the potential of rTMS as a preventive intervention, offering individuals a non-pharmacological option to enhance sleep without the side effects often associated with sleep medications.

Understanding the impact of rTMS on sleep in this demographic could pave the way for larger-scale studies and clinical applications, ultimately contributing to better sleep hygiene and enhanced quality of life for those affected by sleep complaints.

Methodology

Study Design

This open-label pilot study aims to evaluate the effectiveness of repetitive transcranial magnetic stimulation (rTMS) in improving sleep quality among healthy adults with sleep complaints.

An existing literature studying the effects of rTMS on sleep quality and mood in patients with major depressive disorder with similar outcome measures, has sample size of 21. Thus, this study will enrol 30 participants who meet the inclusion criteria.

Participants

30 participants will be recruited from the community through advertisement including universities based on the following criteria:

- Healthy adults aged 18-65
- self-reported sleep complaints

Exclusion criteria include serious mental illness other than primary insomnia, severe neurological conditions, and contraindications for rTMS.

Hypothesis

rTMS significantly improves sleep quality among healthy adults experiencing subclinical sleep issues.

Intervention setting

Participants will undergo a treatment protocol involving six sessions of rTMS using the EXOMIND™ device, administered once or twice a week. Each session will deliver 6,300 pulses at alternating frequencies of 12, 15, and 18 Hz, with a total duration of 24 minutes and 30 seconds. The target site would be left dorsolateral prefrontal cortex (DLPFC), determined by the most common used 5-cm rule. The procedure would be conducted in our research centre with medical staff supported.

Baseline Assessments

The subjects' basic demographic data, including age, gender, years of education, place of birth, marital status, number of children, financial condition, household income, family history of sleep difficulties will be collected upon study entry. Medical history in relation to mental illnesses and medications will also be assessed.

Outcome Measures

Assessments will be conducted at three time points: baseline (pre-intervention), post-intervention, and four weeks post-intervention.

Primary Outcome

Pittsburgh Sleep Quality Index (PSQI): Measures overall sleep quality.

Secondary Outcomes

- Perceived Stress Scale (PSS): Evaluates perceived stress levels.
- Patient Health Questionnaire-9 (PHQ-9): Assesses depressive symptoms.
- Home sleep monitoring: Collects data on sleep duration and sleep stages.

Adverse effects

A checklist of potential adverse effects from TMS administration will be referenced from existing literature to monitor tolerability and adverse events during each session. Blood pressure and heart rate will be recorded at the beginning and end of each session.

Statistical Analysis

Data will be analysed using SPSS version 26.0 or a similar statistical software package.

All the descriptive data including the age and education will calculate means and standard deviations for continuous variables and frequencies and percentages for categorical variables. Repeated measures ANOVA will be used to assess changes in PSQI scores across the three time points (baseline, post-intervention, and 4 weeks post-intervention). Paired t-tests will be conducted to evaluate changes in PSS and PHQ-9 scores, as well as sleep duration and sleep stages recorded by the Apple Watch, between baseline and post-intervention, and between baseline and 4 weeks post-intervention. A p-value of <0.05 will be considered statistically significant.

Impact of the study

This study contributes to the growing body of literature on non-pharmacological interventions for sleep improvement. By focusing on a non-clinical population, it expands the understanding of how rTMS can benefit individuals experiencing everyday sleep disturbances. Results could pave the way for integrating rTMS as a preventive intervention in clinical practice, offering an alternative to traditional sleep medications. This could be particularly beneficial for individuals who are sensitive to medication side effects or those who prefer non-drug therapies. As a pilot study, this research sets the groundwork for larger, more comprehensive trials. Positive findings could lead to further exploration of rTMS applications across different populations and settings, encouraging innovation in sleep disorder treatments.

Handling and storage of personal data and study data

Personal data will be anonymized and kept in password protected computers during and after the study; raw data will be anonymized and kept in locked rooms. Only principal investigator and authorized research assistants will have access to and are responsible for safekeeping of the stored data.

Personal data will be kept for 5 years after completion of study and publications to keep track on potential side effects related to the intervention, and will be destroyed after completion of publications.

Compliance with the ICH-GCP

This study complies with ICH-GCP.

Compliance with Declaration of Helsinki

It declares that the research was conducted according to ethical standards, including the Declaration of Helsinki and its amendments.

Funding

This research received no specific grant from any funding agency in the public, commercial, or not-for-profit sectors.

Conflict of Interest Statement

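### The exclusion criteria exempt primary insomnia, although the aim, hypothesis and impact section claim a subclinical or non-clinical population

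*Protocol*

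**What the plan says.** The Participants section has two inclusion criteria: "Healthy adults aged 18-65" and "self-reported sleep complaints". It then gives the exclusions: "Exclusion criteria include serious mental illness other than primary insomnia, severe neurological conditions, and contraindications for rTMS". This is the only mention of insomnia in the eligibility criteria, and it is an exemption. Neither *healthy* nor *primary insomnia* is defined.

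The population claimed for the study is narrower. The introduction gives the aim as follows: "This research proposal aims to investigate the effects of rTMS on sleep quality among healthy adults experiencing subclinical sleep issues". The Hypothesis section names the same group: "rTMS significantly improves sleep quality among healthy adults experiencing subclinical sleep issues". The section Impact of the study calls the population non-clinical and refers to ordinary, day-to-day disturbed sleep.

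The introduction also draws the line between clinical and subclinical. It says: "Prior research on rTMS and sleep has primarily focused on clinical populations, particularly individuals with insomnia". That sentence goes on to mention sleep disorders that accompany other conditions. The introduction lists clinical insomnia among the mental health conditions in which rTMS has been tried, and it describes growing interest in people whose complaints fall short of clinical insomnia. Directly after stating the aim it adds: "By focusing on this population, we hope to uncover the potential of rTMS as a preventive intervention".

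**The concern.** The study's stated novelty is the move from people with insomnia to people whose sleep problems are below the clinical threshold. The claim of preventive use depends on that move. Eligibility criteria that exempt primary insomnia do not secure it.

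If people with primary insomnia enrol, the main PSQI analysis described in the Statistical Analysis section (a repeated measures ANOVA over three time points) would combine them with subclinical participants. The result would then describe a mixed group rather than the group named in the hypothesis. It would give weaker support, or none, to statements about prevention in a non-clinical population. Who is eligible is fixed by the protocol and cannot be put right once participants are in the study.

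**Working it through.** The protocol gives no figure to reproduce. The check is a comparison of its own statements.

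| Place in the protocol | Population it implies | Position on insomnia |
|---|---|---|
| Introduction, aim | Healthy, subclinical | Outside the claim |
| Hypothesis | Healthy, subclinical | Outside the claim |
| Impact of the study | Non-clinical | Outside the claim |
| Participants, inclusion | Healthy, aged 18-65, self-reported complaint | Not addressed; no upper severity limit |
| Participants, exclusion | No serious mental illness, with one exception | Primary insomnia exempted |
| Title; Study Design | No serious mental illness; healthy with complaints | Silent; counted on neither side |

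**Step 1: does the protocol itself treat insomnia as clinical?** Yes. The introduction places people with insomnia among clinical populations and contrasts them with those who fall short of clinical insomnia. No outside definition is needed.

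**Step 2: does *healthy* settle the matter?** There are two readings.

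- *Healthy* excludes primary insomnia. The exception in the exclusion clause then has no function, and the two sets of criteria conflict with each other.
- *Healthy* does not exclude it. The criteria are then consistent with each other but conflict with the aim, the hypothesis and the impact section.

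Either reading leaves a conflict to reconcile.

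**Step 3: does anything else remove such people?** No. The Baseline Assessments section says "Medical history in relation to mental illnesses and medications will also be assessed", but it attaches no eligibility decision to that history and does not name the participant's own insomnia status.

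**Step 4: how much of the sample could be affected?** The only input is the planned total of 30 (Participants), with no dropout assumed. On the second reading of *healthy*:

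- share per participant = 1/30 = 0.033 = 3.3%;
- range allowed, since no limit is set = 0/30 to 30/30 = 0% to 100%.

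This is the range that the wording permits, not a forecast. The protocol gives neither an expected share of insomnia participants nor PSQI results by insomnia status, so the size and direction of any effect on the PSQI result cannot be derived.

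**The case against.** The strongest reply is that escaping an exclusion is not the same as meeting the inclusion criteria. A participant must still be a healthy adult, and the investigators may take that to rule out insomnia. On this view the exception is a drafting slip, perhaps meant only to say that insomnia is not a serious mental illness. The title and the Study Design sentence are broad enough to fit the exemption, and the impact section also speaks of alternatives to sleep medication and of treating sleep disorders, so it is not uniformly confined to non-clinical use. The introduction's sentence on clinical populations can be read as concerning insomnia that accompanies other conditions. The preventive statements are hopes rather than conclusions. One or two such participants would blur the applicability of a pilot without voiding it, and a SAP could describe results by insomnia status.

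Much of this limits the point without removing it. It is right that eligibility is ambiguous rather than settled, that a small number of such participants would matter little, and that the planned history might pick up insomnia. The lack of a split by insomnia status in the ANOVA is not counted as a fault, because a SAP may deal with it. But a SAP cannot change who is eligible. A drafting slip in the criteria still leaves the person screening without a usable rule. The alternative reading of the sentence on clinical populations does not touch the introduction's separate remark about people short of clinical insomnia, which leads straight into the aim.

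**Conclusion.** The concern holds. The criteria as written do not ensure the population that the aim, hypothesis and impact section claim, and on one reading they openly admit people outside it. Confidence is high that the inconsistency exists; that confidence does not extend to any effect on results.

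The harm is to applicability: a pooled result from a mixed sample would not cleanly address a hypothesis about subclinical adults. A wholly subclinical sample could still be enrolled by chance or by the investigators' own practice, and the conclusion would then be unaffected. The 0 to 30 range in the working assumes that *healthy* does not bar primary insomnia. The point should be fixed, because the repair is cheap before enrolment and eligibility cannot be corrected afterwards.

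**What to change.** Reconcile the passages before enrolment. Which population is intended is for the sponsor to decide.

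- **Route (a), subclinical only.** Delete the exception for primary insomnia. State that people who meet a named definition of clinical insomnia are not eligible, and check this at screening.
- **Route (b), insomnia allowed.** Keep the exception and define primary insomnia. State that *healthy* does not exclude it; the word describes the study population in four places (the aim, the Study Design sentence, the inclusion criterion and the hypothesis). Reword the aim, hypothesis and impact section, including the preventive statements, to cover adults with sleep complaints including primary insomnia. Align the introduction's remark about people short of clinical insomnia. Record insomnia status explicitly in the baseline history already planned, so that the sample can be described.

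Either route needs one protocol amendment. Route (a) adds a screening check and may slow recruitment somewhat. Route (b) costs wording and one item in the history, and leaves a broader but less novel claim.

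### The title, aim and hypothesis assert an effect of rTMS, but one open-label group measured against a single baseline can only show that PSQI changed over time

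*Protocol*

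**What the plan says.** The effect wording stands in three places of the Protocol:

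- Title: "The effectiveness of repetitive transcranial magnetic stimulation (rTMS) on improving sleep quality in adults without serious mental illness".
- Study Design: "This open-label pilot study aims to evaluate the effectiveness of repetitive transcranial magnetic stimulation (rTMS) in improving sleep quality".
- Hypothesis: "rTMS significantly improves sleep quality among healthy adults experiencing subclinical sleep issues".

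The introduction puts the aim more mildly: "This research proposal aims to investigate the effects of rTMS on sleep quality among healthy adults experiencing subclinical sleep issues".

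The design is as follows. Thirty community volunteers with self-reported sleep complaints are enrolled (Participants). All are treated: "Participants will undergo a treatment protocol involving six sessions of rTMS" (Intervention setting). On timing, Outcome Measures says "Assessments will be conducted at three time points: baseline (pre-intervention), post-intervention, and four weeks post-intervention". The Protocol describes no sham, untreated or waiting-list group, no randomisation, and no run-in or repeated baseline. It never uses the term single-arm, but its text allows no other reading.

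Statistical Analysis says of the primary outcome: "Repeated measures ANOVA will be used to assess changes in PSQI scores across the three time points". PSS, PHQ-9 and "sleep duration and sleep stages recorded by the Apple Watch, between baseline and post-intervention, and between baseline and 4 weeks post-intervention" are analysed by paired t-tests. The significance threshold throughout is p<0.05.

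**The concern.** The hypothesis concerns what rTMS causes, whereas the planned test concerns whether mean PSQI is the same at three time points. The two coincide only if nothing but rTMS can move PSQI between baseline and follow-up, and the design gives no ground for assuming that. People enter because they currently complain of poor sleep, so some regression to the mean is possible. The outcome is self-reported and nobody is blinded, so expectation can act. Sleep complaints can also vary with time. Each of these is fully confounded with treatment when there is one group and one baseline.

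What is at stake is the conclusion. The hypothesis says that rTMS significantly improves sleep, and p<0.05 is the only decision threshold given. A significant ANOVA would therefore naturally be reported as confirming the hypothesis, although the same result would follow from a non-specific change of the same size. The paired t-tests do not help, because they too compare only with baseline. The device-recorded measures are less open to expectation but supply no control.

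**Working it through.** **1. Claim against test.** The Protocol offers no figure on this point to reproduce. The sample size of 30 rests on a precedent of 21 in another population, with no effect size, SD or power. The first step is therefore to compare the claim with the test.

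- Claim: rTMS improves PSQI. The matching null hypothesis is that rTMS has no effect on PSQI.
- Test: repeated measures ANOVA in one treated group. Its null hypothesis is equal mean PSQI at baseline, post-intervention and four weeks.
- If rTMS has no effect but the mean changes for another reason, the first null hypothesis is true and the second is false. The 5% error rate protects only the second.

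**2. How small a non-specific change is enough.**

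Inputs from the Protocol: n = 30, three time points, alpha 0.05. Assumptions: complete data, sphericity (equal variances and equal correlation r), and the same mean change d at both follow-ups. The paired t-test is taken as two-sided.

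- Means (0, −d, −d) have grand mean −2d/3, so the sum of squared deviations is (4/9 + 1/9 + 1/9)d² = (2/3)d².
- The error variance is SD²(1−r), so the noncentrality is λ = n × (2/3)d² / [SD²(1−r)].
- The SD of the change score is SD × √(2(1−r)). Writing dz = d / SD of change gives λ = n × (4/3) × dz², which depends on neither the PSQI SD nor r.
- At dz = 0.36, λ = 30 × 1.333 × 0.1296 = 5.18. With 2 and 58 degrees of freedom the critical F is 3.16, and the probability of exceeding it is 50%.

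Chance of p<0.05 when rTMS has no effect and PSQI shifts for other reasons:

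| Non-specific change (SD of change) | ANOVA | One paired t-test |
|---|---|---|
| 0 | 5% | 5% |
| 0.2 | 18% | 19% |
| 0.3 | 36% | 36% |
| 0.5 | 79% | 75% |
| 0.8 | over 99% | 99% |

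For one paired t-test, 50% is reached at 0.37 SD and 80% at 0.53 SD.

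**3. What the study can deliver.** The 95% confidence interval for a mean change has half-width t(29)/√30 = 2.045/5.477 = 0.37 SD of change. That is a usable estimate of within-person change for planning a later trial.

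**4. What the causal wording would require instead.** It would need a concurrent comparator. By the normal approximation, n per arm for 80% power at two-sided 0.05 is 2 × (1.96 + 0.84)² / δ², where δ is the between-group effect in SD. The Protocol gives no δ, so a range is assumed: 175 per arm at 0.3, 63 at 0.5 and 25 at 0.8. Splitting the present 30 into 15 and 15 would give power of about 13%, 28% and 59% respectively.

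**The case against.** The strongest reply is that this is a disclosed open-label pilot. The design sentence says so, and Impact of the study describes groundwork for larger trials. A hypothesis is a proposition to be tested and not yet a conclusion. The analysis sentence speaks only of changes in PSQI, which is accurate. The introductory aim reads as a question, and most of the impact section is conditional. All of this stands, and it is why the point is a matter of wording and not a call for redesign. It does not make the hypothesis testable, because no analysis can supply a missing comparator. Nor does the Protocol anywhere limit a causal reading.

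Four stronger readings are tempting, and the document does not support them:

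- *The false-positive rate is inflated by a known amount.* It cannot be fixed. Entry is by complaint, with no PSQI cut-off, and the Protocol gives no SD, retest correlation or expected drift. The table above shows what a given change would do, not what change will occur.
- *The ANOVA is wrong because it has no direction.* That is true of any omnibus F test. Direction is read from the means, and nobody would report a rise in PSQI as improvement.
- *The ANOVA should give way to another primary analysis.* It answers the question of change over time, so replacing it would be a preference.
- *The impact section overclaims.* Its statements are mostly hedged background and need no edit on this account.

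**Conclusion.** The concern holds as a mismatch between claim and design. The title, the Study Design aim and the hypothesis state a causal effect that one treated group with a single baseline cannot test. On size, a change from any cause of about 0.36 SD of the change score gives even odds of a significant ANOVA at n=30, under complete data, sphericity and equal change at both follow-ups. How likely a non-specific change of that size is cannot be determined from the Protocol, and the conclusion does not depend on it. A reader might infer that the study is invalid or must add a sham arm, but that does not follow. A single-group pilot that estimates change from baseline is a legitimate study. The wording should be corrected because it determines what a significant result will be taken to mean, and correcting it costs almost nothing.

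**What to change.** Keep the single-group pilot, the 30 participants, the visits and the planned ANOVA.

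1. Reword the title, the Study Design aim and the hypothesis to the change in PSQI from baseline to post-intervention and to four weeks after a course of rTMS, as groundwork for larger controlled trials. For the hypothesis, for example: *Mean PSQI changes from baseline to post-intervention and to four weeks after a course of rTMS.*
2. Add one sentence to Statistical Analysis: *A significant change over time in PSQI or any secondary outcome cannot by itself be attributed to rTMS; mean changes from baseline will be reported with 95% confidence intervals.*

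The cost is text edits in four places and a weaker headline claim. Sample size, visits, data collection and the planned tests do not change; the confidence intervals come from data already being collected.

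### The protocol does not say whether or when early stoppers give follow-up PSQI scores, and its repeated measures ANOVA normally uses only participants with all three scores

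*Protocol*

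**What the plan says.** Three parts of the protocol bear on this.

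- **Intervention setting** defines the course: "Participants will undergo a treatment protocol involving six sessions of rTMS using the EXOMIND™ device, administered once or twice a week".
- **Outcome Measures** sets the visits: "Assessments will be conducted at three time points: baseline (pre-intervention), post-intervention, and four weeks post-intervention". The primary outcome is the PSQI. Neither follow-up is given a time from baseline or from the first session.
- **Statistical Analysis** fixes the primary method: "Repeated measures ANOVA will be used to assess changes in PSQI scores across the three time points (baseline, post-intervention, and 4 weeks post-intervention". On software it says: "Data will be analysed using SPSS version 26.0 or a similar statistical software package".

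The protocol does not say what the first follow-up visit means for someone who has fewer than six sessions, or whether such a person is assessed, withdrawn or replaced. It names no completer set, and it does not say that early stoppers are excluded. Study Design calls the trial an open-label pilot, and no control group is described. The planned number is 30.

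**The concern.** Two features act together.

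The first is a gap in data collection. When visits are timed only from the intervention, and the intervention is a six-session course, staff must decide for themselves what to do with a participant who stops after, say, two sessions. One assistant may assess that person straight away and again four weeks later. Another may treat the course as never finished and collect nothing.

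The second is the stated method. Classical repeated measures ANOVA needs a full set of scores from each person. Anyone missing a single PSQI leaves the analysis, and the scores that person did give are not used. This affects early stoppers who are not followed up, and also people who take all six sessions but miss the week-4 questionnaire.

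The within-person change is the whole result here, with no comparator to share or reveal the loss. If people who stop or stop responding tend to have improved less, leaving them out moves the mean PSQI change towards benefit. With 30 participants a few losses count, and the study is meant to prepare for larger trials.

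**Working it through.** **Inputs from the protocol.** Planned number 30, single group; six sessions once or twice a week; three PSQI time points; repeated measures ANOVA; p < 0.05. There is no drop-out rate, expected PSQI change or SD. The 30 is supported only by reference to an earlier study of 21, so there is no planned loss figure to reproduce.

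**Step 1: who stays in the ANOVA.** Under complete-case use, the stated method treats participants as follows.

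| Participant | PSQI scores held | In the ANOVA? |
|---|---|---|
| Six sessions, both follow-ups | 3 | Yes |
| Six sessions, misses week 4 | 2 | No |
| Stops early, assessed at both follow-ups | 3 | Yes |
| Stops early, not assessed | 1 | No |

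The analysed set is people with three PSQI scores, which is not the same as people who completed six sessions. Which of the last two rows an early stopper falls in is what the protocol leaves open.

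**Step 2: does the method need all three scores?** A classical repeated measures ANOVA routine (statsmodels, not SPSS) was given simulated data on 10 people with one score removed. It refused to run, reporting that the data were unbalanced. The person must be dropped or the score imputed first. By contrast, the paired t-tests planned for the secondary outcomes each need only two visits.

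**Step 3: does the protocol imply a date for an early stopper's visits?** Six sessions span five intervals: about 5 weeks at once weekly and 5 × 0.5 = 2.5 weeks at twice weekly. For a full course the first follow-up therefore falls roughly 2.5-5 weeks after the first session, and the second at 6.5-9 weeks (adding 4). No single planned end of course exists from which to date the visits of someone who stops.

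**Step 4: size, on assumed values.** Let *d* be the fraction lost, *m* the mean improvement in those analysed, and *r* the improvement in those lost as a fraction of *m*.

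- Mean in everyone treated = *m* × [1 − *d*(1 − *r*)]
- Overstatement = 1 / [1 − *d*(1 − *r*)] − 1

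With *m* = 3 PSQI points (assumed; the percentage does not depend on it):

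| *d* | Lost of 30 | Analysed | *r* | Mean in all treated | Overstatement |
|---|---|---|---|---|---|
| 10% | 3 | 27 | 0 | 3 × 0.90 = 2.70 | 3/2.70 − 1 = 11% |
| 20% | 6 | 24 | 0 | 3 × 0.80 = 2.40 | 3/2.40 − 1 = 25% |
| 10% | 3 | 27 | 0.5 | 3 × 0.95 = 2.85 | 3/2.85 − 1 = 5% |
| 20% | 6 | 24 | 0.5 | 3 × 0.90 = 2.70 | 3/2.70 − 1 = 11% |

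**Step 5: precision.** For a single paired contrast (two-sided 0.05, 80% power, noncentral *t*; sidedness and power are assumptions), the detectable standardized change is 0.53 with 30 people, 0.56 with 27 and 0.60 with 24. The loss of power is modest, so the main issue is who is left in the analysis.

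**The case against.** The strongest case against is that a reader might infer that the PSQI result will describe six-session completers only, and the protocol does not say that. The first follow-up can fairly be read as falling after the last session received. On that reading someone who stops at session two is assessed then and four weeks later, has three scores and stays in the ANOVA. This objection stands. The protocol permits both readings, so the defect is the missing rule, not a rule that excludes people.

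A second objection is that analysis sets and missing-data handling belong in a statistical analysis plan, which may exist and is not shown. This also stands, and their absence is not criticised here. Two things remain. Whom to assess and when is a data-collection rule, and no later analysis plan can recover scores that were never collected. The ANOVA is a method the protocol states, not a detail it leaves out.

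Two further inferences should not be drawn. The tolerability checklist at each session is routine safety monitoring and does not show that the investigators expect people to stop. Nor is non-completion hidden: the checklist, blood pressure and heart rate are taken at each session, so the number of sessions received should be on record.

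Finally, the 5-25% contains no protocol figure beyond the 30. If people stopped because they were already sleeping well, the bias would run the other way.

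**Conclusion.** The point holds as an ambiguity in follow-up combined with a method that discards partial data. The primary PSQI result risks resting on a selected subset. It cannot be said from the protocol that it will.

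The overstatement of about 5-25% depends on three assumptions: 10-20% of participants are lost, those lost improve by between zero and half as much as the rest, and they leave the ANOVA. The upper end needs both 20% loss and no improvement at all in those lost. The change is worth making before follow-up begins, because uncollected scores cannot be recovered afterwards.

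**What to change.** **Outcome Measures.** State that everyone who receives at least one session is asked for both follow-up PSQI assessments, whatever the number of sessions received. Date early stoppers' visits by one pre-set rule, for example fixed times from the first session, chosen within the range at which those taking the full course are assessed.

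**Statistical Analysis.** Replace the repeated measures ANOVA with a mixed model for repeated measures over the same three time points that includes every treated participant with any PSQI score. Report the number of sessions received and the number of missing scores at each visit.

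The model does not remove the problem by itself. A participant with only a baseline score adds little to the estimated change, and the estimate is sound only if the missing scores can be predicted from those observed. Collecting the scores is therefore the more important half.

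**Cost.** Two sentences of text, a few extra questionnaire contacts, and possibly a slightly less favourable mean change. The sessions and the three time points stay as planned.
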